## 2 RATIONALE

As mentioned above there is very little data on who attends specialist weight management services and how effective the interventions offered in these clinics are. This study will enable us to say

1. Whether there is equal access to treatment based on sex, age, social class and ethnicity and if not start to work out what we can do to ensure this does happen.
2. The characteristics of the people attending the specialist weight management services. This data will give an insight as to how unwell this population is and how many people are being referred to these services which will help with planning of services.
3. How effective these services are and whether this varies from area to area. If we find specific models that are working well we can highlight these to the other clinics.
4. Some insight into the “real world” effectiveness of different types of interventions. This is particularly important with two new obesity drugs now being offered on the NHS.

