#### SfE CORE Study Protocol

2. For the centres entering data to capture data on 60% of the patients attending their clinics.
3. To compare the data entered by 100 patients to that collected by a doctor in their initial interview. This will validate that data entry by patients is reliable.
4. To demonstrate that key outcomes are captured in sufficient quantity to give a fair representation of the people attending the clinics.
5. To describe the demographics and clinical characteristics of people attending the specialist weight management services who sign up to the study.
6. To look at changes in weight and well-being over the time in clinic and whether this is affected by treatment modality.
7. To explore potential disparities in access to specialist weight management services based on demographic factors (e.g., ethnicity, socioeconomic status).
8. To explore potential disparities in outcomes from specialist weight management services based on demographic factors (e.g., ethnicity, socioeconomic status).
9. To explore this methodology in collecting data on these characteristics from those patients who attend weight management services in primary care settings.

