**SfE CORE Study Protocol**

		Relevant Laboratory Results: HbA1c if has diabetes.	months until leaves clinic.
Exploratory	
Demographic and clinical characteristics of people attending clinics.
 
To look at changes in weight and well-being over a year and whether this is affected by treatment modality
 
To explore potential disparities in access to specialist weight management service based on demographic factors (e.g., ethnicity, socioeconomic status).
 
To explore potential disparities in outcomes from specialist weight management service based on demographic factors (e.g., ethnicity, socioeconomic status).
 
To explore the outcomes and data collection within primary care additional to specialist weight management services.
	
All key measures mentioned above
 
Changes in Weight and Wellbeing - Weight, BMI, EQ5D and Body Q scores changes over 12 months. Comparison of these changes between different treatment modalities.
 
Access Disparities: Assess whether certain demographic groups are underrepresented in specialist weight management services
 
Outcome Disparities: Analyse differences in clinical outcomes across various demographic subgroups
 
Expectation: building for the future with expectations of services potentially moving from secondary/tertiary care to primary care sites especially in the role of GLP1 treatments
	
Baseline
 
Baseline and every 12 months.
 
Baseline and every 12 months.
 
Baseline and every 12 months.

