#### SfE CORE Study Protocol

in scope, falling short of achieving a comprehensive national overview. Should this project succeed in gathering adequate data, this system will be commissioned as the NHS-standard platform for such data collection.

Our target is to engage 50% of specialist weight management service to use this system and capture 80% of essential data points for 60% of patients attending these clinics. Each weight management service typically receives approximately 700 patient referrals annually, with patients spending an average of 18 months in the program. We plan to recruit patients for two years, tracking outcomes for the duration of their clinic attendance. Data entry can be retrospective, allowing us in the first year to gather data on approximately 1,050 existing patients ( $700 \times 1.5$ ) and 700 newly referred patients each in the first and second years, leading to a potential recruitment of 2,450 patients per service.

Assuming an 80% capture rate, we anticipate enrolling 1,960 patients per clinic, resulting in a total of 41,160 patients across 21 participating sites.

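### The access-disparity outcome does not separate new referrals from existing patients, so a group's share can reflect length of stay as well as entry

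*Protocol*

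**What the plan says.** Section 2 (Rationale) puts access first among the things the study should show: "Whether there is equal access to treatment based on sex, age, social class and ethnicity", with remedial action to follow if access is unequal. Section 3.1 makes it objective 7. The outcome written for it in section 3.2 (Exploratory) is to "Assess whether certain demographic groups are underrepresented in specialist weight management services".

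Section 6.1 makes any attender at a participating service eligible, not only new referrals. Section 6.2.1 explains who that brings in: "Data entry can be retrospective, allowing us in the first year to gather data on approximately 1,050 existing patients", together with "700 newly referred patients each in the first and second years, leading to a potential recruitment of 2,450 patients per service". The existing-patient figure is the annual referral number multiplied by the average stay, "with patients spending an average of 18 months in the program".

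Appendix 2 places informed consent and the first data collection together at baseline, so for an existing patient baseline falls part-way through treatment. The Data analysis part of section 4 describes the people entered into the database and does not split new from existing patients.

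The exploratory part of the section 3.2 table lists five objectives and four timepoints. The first timepoint is baseline alone and the other three read "Baseline and every 12 months". Read in order, access (third in the list) takes one of those three.

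**The concern.** Rates of entry into a service are best seen among people entering it. A count of people already there depends also on how long each group stays, because those who leave early are gone before they can be enrolled. The outcome is worded as representation in the service, the sample holds a large stock of existing patients, and nothing in the protocol sets new entrants apart. A difference in length of stay could therefore be read as a difference in access.

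The error can go either way. A group with equal entry but shorter stay would seem to face a barrier. A group with a real barrier but longer stay could seem fully represented. Problems of referral and problems of retention call for different responses, and the Rationale says that action should follow from this result.

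**Working it through.** **Inputs from section 6.2.1.** 700 referrals per service per year; mean stay 18 months; two years of recruitment.

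**The plan's own figures.** Existing patients: 700 x 1.5 = 1,050. New referrals: 2 x 700 = 1,400. Total: 1,050 + 1,400 = 2,450, as stated. Existing share: 1,050 / 2,450 = 42.9%.

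**Inputs not in the documents (assumed).** Two groups entering equally, 350 a year each. Mean stays by group are varied with the overall mean held at 18 months. Flow is steady, and enrolment is equally complete in both groups and among new and existing patients, so that a common capture rate cancels out of the shares.

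**Formula.** Existing patients in a group = 350 x mean stay in years. New referrals in a group over two years = 700. Pooled share = (existing + new) / 2,450.

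| Mean stays (months) | Existing, shorter v longer stay | Pooled, shorter v longer stay | Pooled share of shorter-stay group |
|---|---|---|---|
| 18 v 18 | 525 v 525 | 1,225 v 1,225 | 50.0% |
| 15 v 21 | 437.5 v 612.5 | 1,137.5 v 1,312.5 | 46.4% |
| 12 v 24 | 350 v 700 | 1,050 v 1,400 | 42.9% |

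Among new referrals alone the count is 700 v 700 in every row, so the share is 50% whatever the stays.

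**A minority group.** Suppose a group is 20% of referrals and the overall mean stay is 18 months. Its pooled share is (1,050 x 0.20 x d/18 + 1,400 x 0.20) / 2,450, where d is its mean stay in months.
- d = 15: (175 + 280) / 2,450 = 18.6%
- d = 12: (140 + 280) / 2,450 = 17.1%
- d = 9: (105 + 280) / 2,450 = 15.7%

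**Masking.** In the 12 v 24 case the longer-stay group shows 1,400 where equal stays would give 1,225, a ratio of 1.14. With that stay and the overall mean still 18 months, a true entry share 12.5% below par (1 - 1,225/1,400) would appear as full representation.

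**Noise.** At the 41,160 participants projected in section 6.2.1, the simple standard error of a 20% share is sqrt(0.2 x 0.8 / 41,160), about 0.2 percentage points. This ignores clustering by clinic. It shows only that sampling error is unlikely to hide such an artefact, not that the artefact exists.

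**The 12-monthly repeat, conditional.** If the repeat counted only new entrants still attending at 12 months, and stays were exponential, the shorter-stay group's share would be:
- 15 v 21 months: exp(-12/15) / [exp(-12/15) + exp(-12/21)] = 0.449 / (0.449 + 0.565) = 44.3%
- 12 v 24 months: exp(-1) / [exp(-1) + exp(-0.5)] = 0.368 / (0.368 + 0.607) = 37.8%

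If the repeat is a running tally of everyone enrolled so far, nobody leaves the count and this further distortion does not arise.

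**The case against.** The best defence is that the protocol does not state an access analysis at all. It does not restrict the comparison to new entrants, but neither does it say that new and existing patients are pooled for it, and the choice of analysis set for an exploratory aim can be left to a statistical analysis plan that is not shown. Access to treatment can also be read to include staying in it, and representation among service users is a recognisable if crude measure. These points lower the priority. They do not remove the problem: the protocol itself words the measure as representation in the service and itself builds 43% of the potential sample from existing patients.

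A reader might infer more: that the plan fixes a yearly count of those still attending, and so will report retention as access. The documents do not support that. The timepoint comes from matching five objectives to four entries, and although each order-preserving match gives access either the 12-monthly wording or a blank, the alignment is not certain. No text limits the repeat to current attenders. The follow-up rows for the secondary outcome carry a qualifier ending at departure from clinic; the exploratory rows do not. A yearly update of cumulative enrolment is an equally natural reading.

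It is also fair that the sizes rest wholly on assumed stays, and that new referrals, 57% of the potential sample, dilute the effect.

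**Conclusion.** The point holds in a limited form. As written, the access measure mixes entry with length of stay, by the same relation that the plan uses to obtain its 1,050 existing patients. Under equal entry the shorter-stay group's pooled share would be 46.4% (15 v 21 months) or 42.9% (12 v 24 months) instead of 50%. With equal stays it would be exactly 50%. The documents do not say whether stays differ between demographic groups, so they establish that the measure is open to this bias, not that a false disparity will be reported.

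The 12-monthly repeat is an ambiguity to settle rather than a demonstrated error. Because the aim is exploratory, in a study whose primary outcome is the number of clinics using the system, this is a minor point.

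**What to change.** In section 3.2, make the main access comparison on newly referred patients, each counted once at first attendance: about 1,400 potential patients per service in place of 2,450. Show existing patients separately. Clarify the 12-monthly timepoint for this row or remove it. Report the proportion still attending at 12 months, by demographic group, under outcome disparities (objective 8).

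The cost is some rewording, a smaller subset for this one comparison, and a first-attendance date or a flag for new versus existing patients. Sections 3.2 and 4 list no such item; the Data Dictionary named in Appendix 1 is not shown and may contain one.

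The change does not settle two other limits of the access question. Participants are still only those who consent and can use an English-language app, and no reference population is named against which underrepresentation would be judged. People referred who never attend also remain unseen.

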## **4 STUDY DESIGN and METHODS of DATA COLLECTION AND DATA ANALYSIS**

### **Study Design**

This is a multicentre observation study of people attending a specialist weight management service. Data will be collected from two sources

1. the patient who is attending the weight management clinic – they will enter data into a phone app called Peoplewith (<http://peoplewith.com>). This will be the primary source of the data.
2. Weight management services - Healthcare professionals or those with delegated access per site will input data into the clinician portal of the peoplewith app. The data entered will be routine data that is already collected in the clinic.

#### SfE CORE Study Protocol

This study will involve no intervention, no additional clinical visits or changes to care, and no change to usual behaviour or routine.

#### Data collection

Patients will be recruited from weight management services, specialist weight management service in the first instance, via informed electronic consent. Those patients interested in being involved with the study will download an app (*PeopleWith*). Through this app they will learn more about the study and consent to be involved. Once they have consented to being involved, they will be asked to fill in demographic and clinical data on the app and complete some questions. The following data will be collected.

1. **Demographics:** Age, sex, socioeconomic status (derived from postcode), ethnicity, marital status and employment status and Job.
2. **Weight History:** Weight at significant life milestones (birth and leaving school), onset of weight issues, highest and lowest adult weight, weight changes over the past five years.
3. **Previous Weight Loss Attempts:** History of interventions and weight loss with these.
4. **Medical Conditions:** List of medical conditions with dates started. Severity of these medical conditions will be assessed using the Kings score and Edmonton score.
5. **Medication:** Details on dosage and frequency and when started on these drugs.
6. **Patient-Reported Outcomes:** Quality of life (EQ5D questionnaire) and well-being (BodyQ questionnaire).
7. **Clinical Treatments:** Interventions received during clinic visits.
8. **Clinical Measures:** Weight, height, BMI, blood pressure.
9. **Relevant Laboratory Results:** HbA1c if has diabetes.

Every 3 months patients will be prompted to update their records. Patient reported outcomes will be repeated every 12 months or when treatment is changed. See table below explaining in more detail about how the app collects data.

App Registration	New Symptom/Treatment Added	Notifications to Patients
Upon registration there will be a series of mandatory health related data points for the patient to complete	If a patient adds in a new symptom or treatment this will trigger the opportunity to complete a new EQ5D and BodyQ.	Patients will be reminded by notification of the mandatory data points if they have not been completed within 2 weeks of registration
Upon registration there will be available health related data points which are not mandatory for the outcomes of the project, however, there is the opportunity for the patients to		If a patient adds in a new symptom or treatment this will trigger the opportunity to complete a new EQ5D and BodyQ.

#### SfE CORE Study Protocol

engage more in their health care by using the entirety of the app.		
EQ5D and Body Q questionnaire will be available for the patient to complete		Every 3 months patients will be prompted to update their information
Patient support groups pertinent to the care of these patients will be highlighted on a separate tab in the app		

Data from clinic appointments will be entered by healthcare professionals or those with delegated access per site. These people will check the data that the patient has put in and correct if mistakes have been made. In addition, they will enter weight, height and blood pressure readings from the clinic appointments, HbA1c if measured and details on any treatments offered. Finally, they will assess the severity of the patient's medical health using the Kings and Edmonton scores and record this on the *PeopleWith* dashboard. This data entry will be repeated after each clinical visit.

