### **Data Recording and Record Keeping**

The data points collected will be decided upon by the multidisciplinary steering committee, which will include primary care, secondary or tertiary care and patient reported data collection points.

The data will be collected in the *PeopleWith* platform. *PeopleWith* are the digital health technology partner working in collaboration with the Society for Endocrinology, supplying a patient/study participant facing mobile application and site-specific clinical web interface for the capture, consolidation and management of data. All data captured with the *PeopleWith* platform is timestamped and stored securely against the unique identifier of the data creator (patient/study participant or health care professional). *PeopleWith* implement strict data access policies with access recorded and logs retained for the lifetime of the study.

- Sites will have individualised log ins to the platform to input clinical patient related data.

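### Objective 3 does not secure two independent records for its 100 validation patients, so agreement between app entry and doctor's interview can be inflated

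*Protocol*

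**What the plan says.** Section 3.1, objective 3, sets the validation: "To compare the data entered by 100 patients to that collected by a doctor in their initial interview". It gives the purpose in the next sentence: "This will validate that data entry by patients is reliable".

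Section 4 (Study Design) says of the app data: "This will be the primary source of the data". Section 4 (Data collection) then describes the clinic's part: "Data from clinic appointments will be entered by healthcare professionals or those with delegated access per site". Of the same staff it says: "These people will check the data that the patient has put in and correct if mistakes have been made". The paragraph closes: "This data entry will be repeated after each clinical visit".

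Three other places bear on the point:

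- Section 7 (Confidentiality) gives each site a view, on the clinician platform, of the data of its own consenting participants.
- Section 7.6 (Data Recording and Record Keeping) says that all captured data "is timestamped and stored securely against the unique identifier of the data creator", the creator being either the patient or a health care professional. It also leaves patients to choose when they enter data.
- Section 7.6 (Data protection) states that no separate data management document is in use.

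Objective 3 does not reappear in the outcomes table (section 3.2) or in the data analysis text of section 4.

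**The concern.** A reliability check of this kind needs two records made independently of each other. Here one record (the patient's entry) is open to correction by the clinic, and the other (the interview) is made at a clinic that can read the first. Nothing exempts the 100 validation patients from the usual workflow. If discrepancies are removed before the comparison, or never arise because one record informed the other, agreement measures the workflow as well as the patient's accuracy.

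This is the protocol's only stated test of patient-entry reliability. What is at stake is whether its result can be believed.

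**Working it through.** **The plan's own figure.** The number 100 is stated without a target agreement, precision or threshold, so it cannot be reproduced. Section 6.2.1 says no formal power calculation was done. The missing agreement statistic and threshold could sit in an analysis plan and are not counted here.

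**Check of the text.** Independence needs three conditions:

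| Condition | What the protocol offers | Secured? |
|---|---|---|
| The uncorrected entry is compared | Objective 3 refers to data that patients enter. Section 4 has staff correct those data. Section 7.6 time-stamps by creator but does not say that a replaced value is kept or used | No; possibly recoverable |
| The entry is made before the interview | Section 7.6 leaves timing to the patient. Section 4 prompts updates every 3 months. Under the direct approach in section 6.3.1, patients hear of the study in clinic and may be phoned some days later | No |
| The doctor does not see the entry | Section 7 gives the site sight of it. No restriction is stated for the interview | No |

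**Illustration of size.** All inputs except n = 100 are assumptions. Let *t* be the true agreement of the unaided patient entry with an independent interview, and *c* the share of discrepancies removed by correction or copying. Then

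apparent agreement = *t* + (1 − *t*) × *c*.

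For *t* = 0.70 and *c* = 0.5: 0.70 + 0.30 × 0.5 = 0.85.

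| True agreement | c = 0 | c = 0.25 | c = 0.5 | c = 0.75 | c = 1 |
|---|---|---|---|---|---|
| 60% | 60% | 70% | 80% | 90% | 100% |
| 70% | 70% | 77.5% | 85% | 92.5% | 100% |
| 80% | 80% | 85% | 90% | 95% | 100% |

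**Against sampling error.** At *t* = 0.70 and n = 100 the 95% half-width is 1.96 × √(0.70 × 0.30 / 100) = 0.090, about 9 points. The shift from 70% to 85% is 15 points. More patients would shrink the 9 but not the 15.

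**Effect on a pass mark.** Suppose, purely as an assumption, that agreement in at least 80 of 100 counted as reliable. The binomial chance of reaching it is 1.7% at 70% agreement and 93% at 85%.

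**The case against.** The best reply is that objective 3 speaks of data the patients enter, and a value changed by staff is no longer that. With time stamps by creator, the raw entry may well be recoverable, and no passage says that the corrected value is the one compared. This stands in part. If the raw entry is kept and used, inflation from staff correction disappears. It does not reach the other two conditions. A time stamp can show that an entry came after the interview, but it cannot make the two independent, and it says nothing about what the doctor had read.

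A second reply is that the choice of data version belongs in an analysis plan. That is fair for the version. But an analysis plan cannot blind an interview already held or restore a value that was not kept, and section 7.6 rules out a separate data management document.

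A third is that no passage describes a doctor interviewing with the entry on screen. True: the protocol permits it and does not show that it happens.

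A reader might also infer more than the documents support:

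- *That a favourable result follows almost whatever the true error rate.* The formula contradicts this unless *c* is near 1. At *c* = 0.5, true agreement of 70% and 90% appears as 85% and 95%.
- *That this comparison is what justifies the app as primary source.* Section 4 makes the app primary outright. Success is defined by 50% of services and 60% of patients (section 3), and no stated decision depends on objective 3.
- *That existing patients add to the upward bias.* Section 6.2.1 projects 1,050 of them among 2,450 per service, but does not say that any are among the 100. A gap between interview and entry would more likely lower agreement.

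**Conclusion.** The point holds as a gap in the data-collection workflow. For the 100 validation patients the protocol does not fix which version of the entry is compared, the order of entry and interview, or whether the doctor may see the entry. Agreement can therefore be inflated.

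It does not follow that agreement will be inflated, and the documents give no basis for a size. The shift from 70% to 85% rests on an assumed true agreement, an assumed half of discrepancies corrected or copied, and a model in which those steps only turn disagreement into agreement. The 80-of-100 mark is likewise assumed. The change is worth making because it is cheap and must be in place before these data are collected.

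**What to change.** Add one paragraph to section 4 (Data collection), referred to from objective 3, for the 100 validation patients:

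1. Take them from newly referred patients, so that entry and interview fall close together.
2. Have the patient complete the app entry before the initial interview, and lock that time-stamped entry before any staff check.
3. Have the doctor record the initial interview without sight of the app entry.
4. Release the record for staff correction only when both records are locked.
5. State that the locked entry and the locked interview record are the two versions compared.

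The database search in section 6.3.1 already reaches patients on the waiting list, which offers a route to entry before the first appointment. Inclusion criterion 4 requires that the patient is seen in a service, so the paragraph should say whether such patients may consent and enter data beforehand.

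The cost is a record lock and a short delay in staff correction for 100 patients. The validation would also describe new referrals who sign up early, and the report should say so.
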